2.0 Specific Aims

2.1 Specific Aim #1 (primary aim):

- To determine the effect of Doxycycline vs. placebo on the need for additional treatment for unacceptable bleeding at 13 weeks post-randomized treatment.

2.2 Specific Aim #2 (secondary aim):

- To determine if initial treatment with Doxycycline results in higher patient satisfaction with ESI as compared to placebo at 13 weeks post-randomized treatment.

2.3 Specific Aim #3 (secondary aim):

- To determine method continuation and patient satisfaction rate at 26 week post-randomization in patients who choose secondary treatment with Doxycycline for unacceptable bleeding at 13 weeks post-randomized treatment.

In order to evaluate specific aim #1:

- All ESI patients will be offered enrollment in the study at ESI insertion and will begin prospective diaries. They will be contacted at 13 weeks post insertion. If patients report unacceptable bleeding at that time or self-report at any time following an initial 13 week interval, they will be offered randomization to Doxycycline or placebo. Patients will continue a weekly prospective symptom diary for the duration of study.
- Time to recurrence of unacceptable bleeding post-treatment and need for secondary treatment (primary endpoint) will be determined by completion of prospective symptom recording by 13 weeks post-randomized treatment.

- Side-effects and adverse events associated with medical treatment will be documented.

In order to evaluate specific aim #2:

- A patient satisfaction survey will be administered at randomization and 13 weeks post-randomization. The results will be compared between the Doxycycline and placebo study arms.

In order to evaluate specific aim #3:

- Patient satisfaction will be assessed at 13 weeks post-ESI insertion.
- Patients who report unacceptable bleeding after initial randomized treatment and who choose additional treatment will receive secondary treatment with Doxycycline and the method continuation rate and patient satisfaction rate at 26 weeks post randomization will be calculated.
- In patients who leave the study prior to 26 weeks post-randomization, patient satisfaction will be recorded at that time.
- If ESI is removed prior to 26 weeks post-enrollment, the reason, date of removal and alternative contraception will be documented.

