5.2.1 Patient selection

After appropriate IRB approval, ESI users aged 18-51 years old who meet the inclusion and exclusion criteria, and sign a written consent will be **enrolled in the study at the time of ESI insertion**. Every effort will be made to insert ESI on the same day as consent unless medically contraindicated. They will complete a prospective symptom diary from date of ESI insertion. All patients will be contacted by study personnel 13 weeks after enrollment and queried as to the presence of unacceptable bleeding. Bleeding concerns will be objectively assessed using a modification of the Pictorial Blood Loss Assessment Chart (PBLAC) [27]. Patient-initiated contact in with bleeding concerns at any time after 13 weeks post ESI insertion will result in enrollment and randomization at the time of contact. **The basis for randomized treatment will be whether or not the bleeding is “unacceptable” to the patient. This is inherently subjective, but constitutes the basis for most removal requests.** Patients who report unacceptable bleeding at 13 weeks post-ESI insertion, and those who call with bleeding concerns after 13 weeks post ESI insertion, will be randomized into two groups (Doxycycline or placebo). Patients who do not report unacceptable bleeding will continue to complete diaries and may be eligible for randomized treatment if unacceptable bleeding develops. Patients will receive diaries sufficient for completion of the study with instructions to contact study personnel if more diaries are needed or if diaries are lost. Patients and investigators will be blinded to the group assignment as well as the study coordinator who will be responsible dispensing of appropriate study medication by the pharmacy.

Patients who continue to have unacceptable bleeding after 4 weeks post-randomized treatment and wish to have secondary treatment will be treated with Doxycycline. Secondary treatment will not be blinded. Rates of unacceptable bleeding and patient satisfaction scores at 26 weeks post-randomized treatment in remaining study participants will be calculated.

[figure not shown]

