- Normal bleeding frequency (3-5 bleeding episodes).
- Frequent bleeding (more than 5 bleeding episodes),
- Prolonged bleeding (1 or more bleeding episodes lasting 14 days or more)

Subgroup analysis may provide additional insight into the efficacy of treatment for various bleeding patterns.

g. Patient satisfaction surveys

Patients will be asked to fill out short satisfaction surveys at randomization measuring satisfaction prior to any treatment, and at 13 and 26 weeks post randomization (see appendix). If patient has their ESI removed prior to 26 weeks post randomization, she will be given a final satisfaction survey at removal. Patient satisfaction surveys will be recorded on a paper formate or via Mayo Clinic website RED Cap.

Patients will rate their satisfaction with a) ESI and b) bleeding with ESI on a 5-point Likert scale ranging from very satisfied to very dissatisfied. If patient has ESI removed prior to 26 weeks post-study enrollment, she will be given a final satisfaction survey at removal.

h. Treatment issues

At enrollment, patients will be provided with a contact number allowing them to reach study personnel at all times with concerns. Instructions will be provided for instances of drug intolerance/allergy, heavy bleeding or other ESI related issues and clinical appointments for evaluation scheduled as needed.

i. Secondary Treatment

If a patient reports unacceptable bleeding at >4 weeks post randomization to treatment or placebo, study participation will be recorded as **need for additional treatment, and will represent the primary endpoint**. If she wishes to have secondary treatment, she will be treated with Doxycycline. Treatment will be limited to two interventions per 13 week

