5.3.2 Outcome measurements

A. Primary treatment efficacy and safety end point (primary endpoint addressing specific aim #1)

- The efficacy of Doxycycline on ESI-related bleeding will be compared to placebo based on rates of **unacceptable bleeding** and weekly prospective symptom diary at 13 weeks post-randomization.

B. Primary treatment efficacy and safety endpoints (secondary endpoints addressing specific aim #1)

- Method continuation rate at 13 weeks post-randomization will be compared for women in the Doxycycline vs. placebo group.
- Bleeding patterns will be quantified based on the PBLAC and WHO classification of clinically important bleeding patterns over each 13 week reference period.[13,14, 29].
- Incidence of additional symptoms including acne, headache, mood changes in the treatment groups will be compared to placebo at randomization and 13 weeks post-randomization based on the weekly prospective symptom diary
- Interval to recurrence of unacceptable bleeding post-randomized treatment (i.e., need for additional treatment) will be determined
- Rate of adverse events associated with medical treatment will be documented by prospective symptom diary and BMI calculation. These include headache, mood changes, acne and change in BMI.

C. Patient satisfaction with primary treatment endpoint (primary endpoint addressing specific aim #2)

- Patient satisfaction with ESI at randomization for a baseline pre-treatment satisfaction and at 13 weeks post-randomized treatment following primary treatment with Doxycycline vs. placebo will be compared

D. Patient satisfaction with secondary treatment endpoint (primary endpoint addressing specific aim #2)

- Patient satisfaction with ESI at 26 weeks post-randomized treatment for patients with continued unacceptable bleeding following primary treatment who receive secondary treatment with Doxycycline will be calculated.

E. Secondary treatment efficacy and safety endpoint (primary endpoint addressing specific aim #3)

- Method continuation rate at 26 weeks post-randomized treatment for patients with continued unacceptable bleeding after primary treatment who undergo secondary treatment with Doxycycline will be calculated

F. Secondary treatment efficacy and safety endpoint (secondary endpoints addressing specific aim #3)

- Rate of ESI removal for bleeding between 13 and 26 weeks post randomization.

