5.4.1 Power statements

Based on prior Mayo data, we anticipate about 30% of patients will develop unacceptable bleeding following ESI insertion.[3,29] These patients will be approached for participation in this study. The study plans to randomize a total of 100 patients with unacceptable bleeding to either placebo (N=50) or Doxycycline (N=50). The following calculations were based on a two-sided chi-square test with a type I error rate of 0.05.

Aim 1: Of the patients with bleeding concerns, based on our prior experience we anticipate that 44% of the patients randomized to Doxycycline will request additional treatment, and about 80% in the placebo arm. We are purposely overestimating the placebo effect over that noted in our cohort (92% removal requests) to allow for variation in the study group. Given the sample size of 50 per treatment arm, the study will have >90% power to detect the anticipated difference in the need for additional treatment.

Aim 2: Across the two arms, we anticipate that 66 of the 100 patients will request additional treatment and will receive additional treatment with Doxycycline. Within this subset we plan to estimate the method continuation rate following additional treatment. Based on a sample size of 66, the ½ width for a 95% CI around an estimate of 75% is ±10%.

Aim 4: Among the anticipated 66 patients who will request additional treatment for continued unacceptable bleeding at 26 weeks post-ESI insertion, we plan to quantify the patient satisfaction rate. If we assume 75% will be “very satisfied” or “satisfied”, then the ½ width for a 95% CI around this estimate will be ±10%.

5.4.2 Proposed Statistical Analysis:

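### The single Aim 3 rates mix women taking doxycycline for the first time after placebo with women repeating it after doxycycline, and estimate neither group's rate

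*Combined protocol and SAP*

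**What the plan says.** Section 2.3 sets Aim 3 as continuation and satisfaction at 26 weeks after randomization "in patients who choose secondary treatment with Doxycycline for unacceptable bleeding at 13 weeks post-randomized treatment". Two sections decide who enters that group:

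- Section 5.3.1 i opens with "If a patient reports unacceptable bleeding at >4 weeks post randomization to treatment or placebo" and continues "If she wishes to have secondary treatment, she will be treated with Doxycycline". Women from either arm can enter, and all of them receive the same drug.
- Section 5.2.1 adds "Secondary treatment will not be blinded".

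Section 5.3.2 D (satisfaction) and E (continuation) each define one group. Under E the rate for women "who undergo secondary treatment with Doxycycline will be calculated", with no reference to original arm.

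Section 5.4.1, under the label Aim 2, makes the pooling explicit: "Across the two arms, we anticipate that 66 of the 100 patients will request additional treatment". It plans one continuation rate in that subset, with a 95% interval of ±10% around 75%. The paragraph labelled Aim 4 does the same for satisfaction. Section 3.3 sets one success criterion, continuation above 75%. Section 5.4.2 plans confidence intervals for continuation and satisfaction and names no split of this subset.

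**The concern.** A woman whose placebo course failed takes doxycycline for the first time. A woman whose doxycycline course failed repeats a drug that has just not worked for her. These are different clinical questions and may have different answers. Section 5.3.1 i itself gives assessing the efficacy of each doxycycline course as its reason for limiting the number of interventions, yet no planned analysis separates first from repeat use.

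The weights in the pooled rate are the numbers of failures in each arm, and failure is the primary outcome. If the two groups continue the method at different rates, the Aim 3 result depends partly on how the primary comparison turns out. A pooled rate above 75% could then rest mainly on women who had never taken doxycycline before.

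**Working it through.** **Inputs.** All are from section 5.4.1 unless marked.
- 50 women per arm.
- Need for additional treatment: "we anticipate that 44% of the patients randomized to Doxycycline will request additional treatment, and about 80% in the placebo arm".
- Stated pool of 66, assumed rate 75%, stated half-width ±10%.
- Success criterion above 75% (3.3), treated here as applying to the point estimate.
- Continuation rates by type of course: not given in the documents, so assumed below over a range.

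**Step 1. The plan's precision figure.** Half-width = 1.96 × √(p(1−p)/n). With p = 0.75 and n = 66: 1.96 × √(0.1875/66) = 10.4 points. This reproduces the stated ±10%.

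**Step 2. Composition of the pool.**
- Placebo failures: 0.80 × 50 = 40.
- Doxycycline failures: 0.44 × 50 = 22.
- Total: 62, of which 40/62 = 65% are first-time users and 22/62 = 35% repeat users.

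The stated 66 does not follow from these rates. With 22 doxycycline failures it would need 44/50 = 88% failure on placebo. At n = 62 the half-width is 10.8 points. If 66 is kept with 22 doxycycline failures, the split is 44:22, or 67% first-time users, so the picture hardly changes. These counts are upper limits at the plan's rates, because secondary treatment is optional and some women may have the implant removed instead (5.3.1 i).

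**Step 3. Dependence on the mix.** Pooled rate = (n₁p₁ + n₂p₂)/(n₁ + n₂), where 1 is first course after placebo and 2 is repeat course after doxycycline. The total is held at 62. The p₁ and p₂ values are assumptions. The mixes 35:27 and 45:17 correspond to failure rates (placebo/doxycycline) of 70%/54% and 90%/34%.

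| Assumed p₁ / p₂ | 35:27 | 40:22 | 45:17 |
|---|---|---|---|
| 75% / 75% | 75.0% | 75.0% | 75.0% |
| 80% / 65% | 73.5% | 74.7% | 75.9% |
| 85% / 57% | 72.8% | 75.1% | 77.3% |
| 90% / 48% | 71.7% | 75.1% | 78.5% |

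For the third row: (35 × 0.85 + 27 × 0.57)/62 = 45.14/62 = 72.8%, and (45 × 0.85 + 17 × 0.57)/62 = 47.94/62 = 77.3%.

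Down the middle column, a pooled rate of about 75% fits four quite different pairs. Across each of the last three rows, the rate crosses 75% although neither group's own rate has changed. Across the first row nothing moves.

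**Step 4. Precision by original arm, at 75%.**
- After placebo, n = 40: 1.96 × √(0.1875/40) = 13.4 points.
- After doxycycline, n = 22: 1.96 × √(0.1875/22) = 18.1 points.
- Difference between the two: 1.96 × √(0.1875 × (1/40 + 1/22)) = 22.5 points.

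**The case against.** The strongest reply is that Aim 3 asks about everyone who chooses secondary treatment, and the pooled rate answers that question. This stands. A reader might infer that the pooled rate answers no useful question, and the documents do not support that: in this protocol secondary treatment means open-label doxycycline after either randomized treatment, and the pooled rate describes that policy. What it does not give is either course-specific rate.

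A reader might also infer that the Aim 3 rate must move with the primary result. It moves only if the two groups' true rates differ. The documents give no such rates, so the size of the effect is assumed. Under 85%/57% the swing from 72.8% to 77.3% is 4.5 points, smaller than the sampling half-width of about 10.8 points. Nor does the plan say that a good pooled rate would support repeat courses; that is a possible misreading by others.

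The plan does contain by-arm language. Section 5.4.2 says that patients are analyzed by randomized arm and lists satisfaction items among the between-arm comparisons. Section 8.4 expects by-arm removal and satisfaction results at 26 weeks. These statements concern whole arms, not the retreated subset, and 5.4.1 specifically sizes one estimate across both arms. They do not close the gap.

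Finally, about 22 repeat users is a small group, and both groups are selected by failure after randomization. Section 5.3.1 i allows up to two interventions per 13-week interval, so by 26 weeks some women may have had more than one open-label course. This limits what the split can show and affects how its rows should be labelled, but pooling does not remove the imprecision.

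**Conclusion.** The point holds, as a minor one. The single continuation and satisfaction rates combine at most about 40 first-time and 22 repeat users, so roughly two thirds of the pool says nothing about repeating doxycycline after it has failed. The pooled figure is valid for the broad policy of offering doxycycline to those still bleeding, but not as an estimate for either group.

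The composition rests on the plan's 44% and 80% and on every failure accepting secondary treatment. Any effect on the 75% criterion rests on assumed unequal continuation rates; with equal rates there is none. The mismatch between 62 and 66 needs correcting but does not alter the conclusion. Aim 3 is secondary, uncontrolled and descriptive, and the primary comparison is unaffected.

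**What to change.** In 5.3.2 D and E and in 5.4.2:

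- Report Aim 3 continuation and satisfaction by original randomized arm, each with a 95% confidence interval. Label the rows *open-label doxycycline after placebo* and *open-label doxycycline after doxycycline*, since a row may include women with more than one open-label course.
- Keep the pooled rate as an overall summary, and say that it will not be used alone to support repeat courses.
- State that the two rows are descriptive subgroups selected after randomization and that differences between them are not a randomized comparison.

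In 5.4.1, reconcile the stated 66 with the 62 implied by 44% and 80% of 50, and add the expected by-arm precision.

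The cost is two table rows per outcome and a few sentences. No new data are needed, because original assignment is available once the data are unblinded (5.3.1 j). The downside is wider intervals: about ±13 and ±18 points at 75%, against about ±10 for the pooled rate.

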5.4.1 Power statements

Based on prior Mayo data, we anticipate about 30% of patients will develop unacceptable bleeding following ESI insertion.[3,29] These patients will be approached for participation in this study. The study plans to randomize a total of 100 patients with unacceptable bleeding to either placebo (N=50) or Doxycycline (N=50). The following calculations were based on a two-sided chi-square test with a type I error rate of 0.05.

Aim 1: Of the patients with bleeding concerns, based on our prior experience we anticipate that 44% of the patients randomized to Doxycycline will request additional treatment, and about 80% in the placebo arm. We are purposely overestimating the placebo effect over that noted in our cohort (92% removal requests) to allow for variation in the study group. Given the sample size of 50 per treatment arm, the study will have >90% power to detect the anticipated difference in the need for additional treatment.

Aim 2: Across the two arms, we anticipate that 66 of the 100 patients will request additional treatment and will receive additional treatment with Doxycycline. Within this subset we plan to estimate the method continuation rate following additional treatment. Based on a sample size of 66, the ½ width for a 95% CI around an estimate of 75% is ±10%.

Aim 4: Among the anticipated 66 patients who will request additional treatment for continued unacceptable bleeding at 26 weeks post-ESI insertion, we plan to quantify the patient satisfaction rate. If we assume 75% will be “very satisfied” or “satisfied”, then the ½ width for a 95% CI around this estimate will be ±10%.

5.4.2 Proposed Statistical Analysis:

Patients will be analyzed according to their randomized treatment arm. All calculated p-values will be two-sided and p-values less than 0.05 will be considered statistically significant. Analyses will be performed using SAS software package (version 9.2). Comparisons of categorical endpoints (e.g. need for additional treatment, bleeding pattern based on the WHO classification, presence of adverse event(s), satisfaction survey questions) between the two arms will be evaluated using the chi-square test. Additional comparisons of these endpoints, adjusted for potential confounders, will be assessed by fitting separate logistic regression models. Time-to-event methodology (e.g. Kaplan-Meier method and Cox proportional hazards regression models) will be utilized for binary versions of these endpoints if patient follow-up becomes an issue and patients don't comply with the planned follow-up before completing the study. Poisson regression models will be used to compare the diary responses between the treatment arms. In the Poisson model, the endpoint will be the number of bleeding and spotting days per patient (and likewise the number of days with additional symptoms), offset by the total days of diary follow-up per patient. Ninety-five percent confidence intervals (95% CI) will be constructed around the estimates for method continuation and satisfaction.

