interval to allow for assessment of efficacy of each course of Doxycycline. Rates of unacceptable bleeding in all patients remaining in the study at 26 weeks post-randomization will be calculated and participation in the study will end. If patients request ESI removal at any time during the study after randomly assigned treatment, study participation will be recorded as a **removal**. Method satisfaction will be assessed at removal and study participation will end. Patients will be provided with alternative contraception of choice at their expense. **Need for additional treatment at >4 weeks post-randomized treatment will represent the primary endpoint.** Satisfaction with ESI at randomization, and 13 and 26 weeks post randomization, and method continuation at 26 weeks post-randomization represent the secondary endpoints.

j. Post-treatment Followup

All patients will be contacted by study personnel at 26 weeks (\pm 2 weeks) post-randomization for final satisfaction survey and weight. Study completion BMI will be calculated. All diaries will be collected for analysis and patients will receive remuneration. When all patients complete the study, the data will be unblinded for analysis.

k. Special Considerations

If patients receive randomized treatment toward the end of the 39 week study interval (rather than at about 13 weeks post ESI insertion), post-treatment data for at least 13 weeks will be collected for a maximum study length of 52 weeks post-ESI insertion.

l. Additional testing

Additional laboratory testing or imaging for heavy or unusual bleeding will be individualized as clinically indicated.

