7.1 Study Duration

Patients will be offered enrollment in the study upon ESI insertion. They will begin completing weekly prospective symptom diaries at that time. If they report unacceptable bleeding at the time of study personnel contact at 13 weeks post ESI insertion or self-report unacceptable bleeding at > 13 weeks post ESI insertion, they will be offered randomization to Doxycycline or placebo. They will continue prospective weekly symptom diaries for 26 weeks post randomization or until they discontinue study participation. A patient who self-reports unacceptable bleeding late in the study interval will be followed for at least 13 weeks after randomized treatment in order to have a meaningful study conclusion. The maximum study length for such a patient would be 52 weeks from ESI insertion. Based on current numbers of ESI insertions per year, **we anticipated that all 100 subjects with unacceptable bleeding will randomized within 30 months. However, the rate of reported unacceptable bleeding was lower than expected and therefore we propose an additional enrollment of 120 patients (total 470 patients) to achieve 100 randomized patients.**

8.0 Study Expectations and Limitations:

This study is a double blinded placebo-controlled randomized prospective trial of Doxycycline for the management of ESI-related unacceptable bleeding. The study will include US women regardless of BMI. Randomization will be done using a dynamic

allocation process with stratification by age, BMI and postpartum status. This will avoid confounding effects of these variables on our outcomes.

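### Section 5.4.1 bases the secondary-treatment precision on 66 women where its own rates give an expected 62 (about ±11%, not ±10%), and the 52-week cap leaves some late-randomized women without a 26-week continuation result

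*Combined protocol and SAP*

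**What the plan says.** Section 5.4.1 plans 50 women per arm. For Aim 1 it states: "we anticipate that 44% of the patients randomized to Doxycycline will request additional treatment, and about 80% in the placebo arm". The next paragraph, labelled Aim 2, sizes the secondary-treatment group: "Across the two arms, we anticipate that 66 of the 100 patients will request additional treatment". With n = 66 it gives a 95% half-width of ±10% around a continuation rate of 75%. The paragraph labelled Aim 4 reuses the count for satisfaction ("Among the anticipated 66 patients who will request additional treatment for continued unacceptable bleeding at 26 weeks post-ESI insertion") with the same ±10%.

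Section 5.3.2.E sets the Aim 3 endpoint as method continuation 26 weeks after randomized treatment among women given secondary doxycycline. Section 3.3 treats a rate above 75% as support for the hypothesis.

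On follow-up, 5.3.1.j states: "All patients will be contacted by study personnel at 26 weeks" after randomization, with a window of two weeks either way. For women randomized late, 5.3.1.k instead provides that "post-treatment data for at least 13 weeks will be collected for a maximum study length of 52 weeks post-ESI insertion". Section 7.1 repeats the limit: "The maximum study length for such a patient would be 52 weeks from ESI insertion".

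**The concern.** There are two separate problems.

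First, the 66 does not follow from the rates stated one paragraph above it. The precision given for both continuation and satisfaction rests on that count and so is slightly too favourable.

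Second, the plan sets an endpoint at 26 weeks after randomization but stops some women earlier by design. Section 3.3 compares the continuation rate with a threshold, so it matters how women whose follow-up ends at the cap with the implant in place are counted. Counting them as continuing pushes the rate up. Leaving them out while still counting late-randomized women who had a removal pushes it down. Secondary treatment is open-label (5.2.1) and the estimate pools both arms, so blinding to the randomized assignment does not protect this choice if it is made after the data are seen.

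**Working it through.** **Inputs.** 44%, about 80%, 50 per arm, 66, 75%, ±10% and two-sided 0.05 are from 5.4.1. The 26-week endpoint is from 5.3.2.E, the ±2-week window from 5.3.1.j, and the 52-week cap and 13-week minimum from 5.3.1.k and 7.1.

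**The plan's figure at n = 66.** Wald half-width = 1.96 × √(0.75 × 0.25 / 66) = 10.45 points; Wilson 10.25. Both round to ±10%, so the precision is right for 66 and the error lies in the count. Section 5.4.2 does not name an interval type. Clopper-Pearson gives 11.0 at n = 66, so it was evidently not the method used.

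**Expected count from the Aim 1 rates.** 0.44 × 50 + 0.80 × 50 = 22 + 40 = 62. Exactly 66 would need 88% on placebo, (66 − 22)/50, or 52% on doxycycline, (66 − 40)/50. The 92% cohort figure gives 22 + 46 = 68, but 5.4.1 sets it aside in favour of 80%.

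**Half-width at n = 62.** Wald: 1.96 × √(0.1875 / 62) = 10.78 points; Wilson 10.56. Both round to ±11%. The change is about 0.3 points on either method.

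**Spread of the count.** SD = √(50 × 0.44 × 0.56 + 50 × 0.80 × 0.20) = √20.32 = 4.5. From the two binomials, P(66 or more) = 0.22 and P(more than 62) is about 0.46.

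**Aim 1 power.** Pooled rate 0.62; null SE = √(2 × 0.62 × 0.38 / 50) = 0.0971; alternative SE = √((0.44 × 0.56 + 0.80 × 0.20)/50) = 0.0902. Power = Φ((0.36 − 1.96 × 0.0971)/0.0902) = 97.0%. The stated figure of above 90% holds.

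**Follow-up under the cap.** Available weeks = 52 − week of randomization:

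| Week randomized | Maximum weeks after randomization |
|---|---|
| 13 | 39 |
| 26 | 26 |
| 28 | 24 (earliest edge of the window) |
| 30 | 22 |
| 39 | 13 |

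After week 26, or week 28 using the window, the 26-week assessment falls beyond the cap. A removal before the cap is still a known outcome. Only women still using the implant at the cap lack a result.

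**Rules that come close.**
- Section 2.0 records satisfaction when a woman leaves early, but does not address continuation.
- Section 5.2.1 uses women still in the study as the 26-week denominator for bleeding and satisfaction. That cannot yield a continuation rate, because 5.3.1.i says of removals: "Method satisfaction will be assessed at removal and study participation will end".
- Section 5.4.2 offers Kaplan-Meier and Cox methods when patients fail to adhere to scheduled follow-up. A planned cap is not non-adherence, and continuation is not among the example endpoints.

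**Sensitivity to the rule (all inputs assumed).** Take 62 women, 12 of them late, 75% continuation among the 50 early women (37.5), and 2 removals seen among the late women.
- Late women counted only if removed: 37.5/52 = 72%.
- Late women at the cap counted as continuing: (37.5 + 10)/62 = 77%.
- Early women only: 37.5/50 = 75%.

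The rule alone can move the estimate across 75%. This shows sensitivity and is not a forecast.

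**The case against.** The arithmetic gap is small. It shows only because 10.45 and 10.78 fall on either side of a rounding boundary. The placebo input is only approximate, 66 lies between the 62 and 68 given by the two placebo rates mentioned in 5.4.1, and it is within one SD of 62. No sample size or test depends on it. All of this stands and is why the point is minor. It does not make 66 consistent with the adopted rates.

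On the cap, the plan already names Kaplan-Meier methods, and 10.1.1 foresees only a limited number of late-randomized women needing contact beyond week 39. This also stands in part: the remedy is to extend an existing sentence, and the number affected may be small.

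Three stronger readings are tempting, and the documents do not support them.
- A reader might infer that 62 is a ceiling, because secondary treatment is optional ("If she wishes to have secondary treatment, she will be treated with Doxycycline"). But 62 is an expected value, exceeded with probability about 46%, and the 44% and 80% already describe women who ask for treatment. Discounting again for choice would count it twice.
- A reader might infer that every late-randomized woman is lost to the endpoint. Those with a removal before the cap are not.
- A reader might infer a material loss of precision. If 10% or 20% of the 62 were left out, n would be 56 or 50 and the Wald half-width 11.3 or 12.0 points. Those shares are assumed, since the documents give none, so these figures are illustrative only.

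**Conclusion.** Both parts hold, at minor severity. On the rates adopted in 5.4.1, the expected secondary-treatment group is 62, and the 95% half-width at 75% is about ±11% for continuation and for satisfaction. This assumes a Wald or Wilson interval and that all 62 contribute data.

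The 52-week cap conflicts with the 26-week endpoint and with the statement that all patients are contacted then. It leaves no 26-week continuation result for women randomized after about week 26 (week 28 with the window) who still have the implant at the cap. No section says how they count. The size of that effect cannot be stated, because the timing of randomizations is not given.

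A reader might infer that the primary comparison is weakened. It is not: Aim 1 power stays at about 97%, and the point concerns only a secondary, single-group estimate.

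**What to change.** 1. In 5.4.1, replace 66 with an expected 62 (22 + 40) and ±10% with about ±11%, for continuation and for satisfaction, and name the interval method.
2. Reconcile 5.3.1.j, 5.3.1.k, 5.3.2.E and 7.1, so that it is clear which women have a 26-week assessment.
3. Before any 26-week data are summarized, and no later than unblinding, fix one rule for the 75% criterion that does not depend on outcome. The smallest change is to extend the Kaplan-Meier provision in 5.4.2 to method continuation, with women censored at the planned cap. Late women are then neither counted as continuing nor counted only when they have a removal, and every woman is kept. This assumes that the timing of randomization is unrelated to the chance of removal. A simple proportion among women randomized before a pre-set week is an alternative that avoids the assumption, but it loses women and describes only the early-randomized group. Either rule should also say how withdrawal without a recorded removal is treated.
4. As an editorial matter, align the aim labels in 5.4.1 (Aim 2, Aim 4) and 5.3.2.D with section 2.0, which lists this content under Aim 3 and has no Aim 4. Give one date for the outcome in 3.3: 39 weeks after insertion and 26 weeks after randomization coincide only for randomization at week 13 (39 − 26). Say what the 26 weeks after insertion in the Aim 4 paragraph refers to.

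The cost is wording only, with no added patients or contacts under the Kaplan-Meier option. The stated half-width rises by about 0.3 points.
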